HMC RESEARCH PROTOCOL

Nurse-led medication self-management intervention in the improvement of medication adherence in adult patients with multi-morbidity: A Feasibility Randomized controlled trial

[name]

[name]

Date-2 Nov 2022

NCT- Not available

1. Summary

Back ground & Aims

Adult patients suffering from multimorbidity are at high risk of medication non-adherence. It has been well established that self-management support is an effective strategy to enhance medication adherence for patients with chronic conditions. However, little is known about the effect of the medication self-management intervention in Adult patients with multimorbidity. The aim of this study to evaluate the effectiveness of a nurse-led medication self-management intervention in improving medication adherence and health outcomes in adult patients with multimorbidity.

Methods

This study is a single centre, single-blind, two-arm randomised controlled trial. Adult patients with multi-morbidity will be recruited from NCCCR Qatar. A total of 100 participants will be randomly allocated to receive standard care or standard care plus the medication self-management intervention. The intervention will be delivered by clinical nurse specialists. The 6-week intervention includes three face-to-face education sessions (2st week, 4rd week and 6th week) and two weekly (8th week and 10 week) follow-up phone calls. Participants in the control group continue to receive all respects of standard care offered by healthcare providers, including chronic disease management, drug prescription, referral to hospital specialists, health education and consultations regarding patients' diseases and treatments during centre visits.

Outcome

The primary outcome is medication adherence as measured by the 5-item Medication Adherence Report Scale. Secondary outcomes include medication self-management capacity (medication knowledge, medication beliefs, and medication self-efficacy), treatment experiences (medication treatment satisfaction and treatment burden). All outcomes will be measured at baseline, immediately post-intervention (7th week), and at 3-month post-intervention.

2. Abbreviations and Acronyms

NCCCR- National Cancer Care Center and Research

CNS- Clinical Nurse Specialist

IMB- Information-Motivation-Behavioral Skills

3. Introduction / Background

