
evoking, focusing, planning and motivational interview process. The current study aims to implement evidence-based, theoretical and nurse-led drug self-management interventions in adult patients with multi-morbidity.

4. Objectives

The primary objective

To evaluate the effectiveness of a six-week intervention led by a nurse in medication self-management to improve medication compliance in adult patients with multimorbidity and going to discharge, as compared with standard care.

[figure not shown]
Secondary objectives

To evaluate the effectiveness of the intervention on the improvement of patients' medication self-management capacity (medication knowledge, medication beliefs, and medication self-efficacy), treatment experiences (medication treatment satisfaction and treatment burden), as compared with standard care. *(Retrospective means the data is already in existence when the project is submitted to the IRB for initial (if this is a retrospective chart review, the end date must come before the submission date): mm/dd/yyyy to mm/dd/yyyy)*

5. Study Methodology

This is a single Centre open label, two-arm randomized controlled trial with 1:1 randomization at the participant level. The patient population will be patients with at least two comorbidities. The patient recruitment will be done in the National Centre for Cancer Care and Research (NCCCR) in the outpatient department in the clinical nurse specialist counselling room. Participants will randomly be allocated to receive standard care(control) and standard care plus the medication self-management intervention (Motivational Interview). Primary and secondary outcomes of study will measure better medication adherence, medication self-management capacity and treatment experiences, which will be collected from both group including the intervention group and control group (Participants in the control group will continue to receive all respects of standard care offered by healthcare providers) at baseline (T0), in the 7th week immediately post-intervention (T1), and at 3-month post-intervention (T2). This protocol is presented based on the recommendations of the Standard Protocol Items: Recommendations for Interventional Trials (SPIRIT) 2013 statement(24). The results of this trial will be reported as per the Consolidated Standards of Reporting Trials (CONSORT) 2010 statement(25).

An overview of the study design is shown in Fig. 1.

[figure not shown]

Fig. 1 CONSORT flow diagram of the study protocol

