Three clinical nurse specialist as a part of research team from NCCCR will deliver the intervention. Nurses' inclusion criteria are (1) Senior clinical nurses with a Master degree or above, (2) having at least 3 years of working experience in HMC, (3) taking on chronic disease management in routine work, and (4) not planning to quit the job in the next 6 months and Nurses who are participating in other research studies on chronic disease management at the time of this study will be excluded. Nurses will recruit participants through approaching potentially eligible participants in NCCCR. Centre appointments by Clinical nurse specialists will be arranged for interested participants and the principal investigator/ co-investigator will determine the eligibility of participants, describe the study to them, obtain written consent forms, and collect baseline data. A one-week period will be allowed for participants to decide whether or not they wish to participate in the study. Participants' reasons for nonparticipation will be recorded.

Sample size; data collection methods

Sample size

Sample size calculation was performed using G*Power Version 3.1.9.7. Estimation is based upon the primary outcome, medication adherence, at 3 months of follow-up between the intervention and control group. Medication adherence is calculated as sum of the scores from each item using Morisky 8. Based on our recent systematic review and meta-analysis on medication adherence interventions among patients with multimorbidity Cohen's effect size (d) of 0.52 on medication adherence is estimated for a medication self-management intervention program. The required sample size will be 94 participants (47 in the intervention group and 47 in the control group) to attain an 80% power with a two-sided α of 0.05. Therefore, for a 5% attrition rate, the final sample size required is 100 participants.

For Arabic speaking patients, the questions will be translated to Arabic by the Arabic speaking research team member.

Randomization & blinding

Consenting participants will be randomized in outpatient clinic in NCCCR. Randomization will be block randomization, and generated by a computer program centrally (Nursing/ Midwifery Research department).

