Following recruitment, patients will be randomized to either the intervention or the control arm in a near 1:1 ratio, using a computer-generated randomized permuted block design. The design will use random block lengths of 2, 4 or 6, and include an initial unbalanced block, with a maximum of one additional patient in either arm, to further hide allocation sequences, which means that the ultimate sample size and allocation ratio will vary very slightly from what is planned depend on the unbalanced block.

Each participant will be assigned a special code generated by the computer. The randomization will be kept by the PI and CNS. After the eligibility assessment by CNS, data will be obtaining at the baseline (after completion of informed consent), 7th week and 12th week.

Intervention group

The medication self-management intervention consists of three face-to-face education sessions and two weekly telephone follow-up over 6 weeks. Intervention components are derived from an extensive review of the literature, including the related theoretical framework and current practice. Based on the extended IMB model of medication adherence, this intervention is designed to offer information related to medication treatment, motivate patients to adhere, help build medication self-management skills, and develop adherence improvement plans. The face-to-face meeting will take place in the clinical nurse specialist counselling room in NCCCR. The face-to-face sessions will include all of the following: exploration of medication treatment experience and expectation, medication knowledge education, motivation feedback tailored to the individual's personal and social barriers to adherence, medication self-

management skills building, and goal setting. A patient-centered approach will be adopted considering the complex needs of patients with various combinations of chronic conditions.

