- ❖ Personalized feedback

Nurses' training Intervention

[figure not shown]
The certified clinical nurse specialists will be informed of the study objectives, procedure, detailed intervention protocol, and ethical considerations. Training sessions will involve medication self-management support, teach-back techniques, shared decision making, and basic motivational interviewing skills, e.g., posing open-ended questions, reflective listening, and expressing empathy(32). Nurses will also receive a detailed study protocol and a manual containing instructions for delivering the intervention.

7. Study procedures

Provide an outline and describe in detail the processes and operations of the study, including logistics

Study Duration and Timelines

The evaluation of the project process will be against the key milestones as described below.

Informed Consent

a) *How people will be **NOTIFIED OR APPROACHED** to consider being a research subject in this study?*

During the OPD visit of the patient the CNS will approach the patients directly based on the inclusion exclusion criteria. All the study details will be explained to the patient in detail at the CNS office. After explaining the study details to the patients, a minimum of one-week time will be given to them before they are decided to take part in the study. After the written informed consent patient will be enrolled to the study and allocated randomly to control and intervention group. **For Arabic speaking patients, the informed consent form will be translated in Arabic by the Arabic speaking research team member.**

b) *Describe the **CONSENT PROCESS** procedures (When, Where, How, by Whom).*

CNS will approach the patients directly based on the inclusion exclusion criteria. All the study details will be explained to the patient in detail at the CNS office. After explaining the study details to the patients, a minimum of one-week time will be given to them before they are decided to take part in the study. We will contact the patient to confirm their participation in the study. If they agreed to participate in the study, will advise to come to the outpatient visit for face to face interview.

c) *Describe **HOW LONG** potential participants will have to decide on participation.*

1 week

d) *Describe how subjects will be **SCREENED FOR ELIGIBILITY** for the study.*

Based on Inclusion and exclusion criteria

e) *Describe how subjects will be **ENROLLED** into the research study below.*

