Based on screening & randomization tool

Risk

In this section describe the anticipated risks associated with participation in the research (i.e. illness, injury, death)

No risk is anticipated as part of study

Bio-Specimens & Sample Collection

In this section describe what specimens or samples will be collected specifically for research, if specimens will be stored long-term and/or destroyed. Consider what happens to data/specimens if subject withdraws consent

NA

Outcomes

In this section provide details on the outcome measures and the anticipated primary & secondary outcomes

Outcome assessment

The nurses masked to the participant allocation will collect follow-up data through telephone interview. Participants will be assessed at baseline (T0), in the week immediately post-intervention (7th week) (T1), and at 3-month post-intervention (T2). Table 2 provides an overview of primary and secondary outcomes as well as covariates at each time point. Permission will be obtained from the original authors to use the scales for this study.

Primary outcome

Medication Adherence

The English version of Morisky-8 will be administered to assess medication adherence of the participants(29). The Morisky-8 is a self-reporting measure of unintentional and intentional medication non-adherent behaviors with a yes and no response. The total score of the moresky-8 ranges from 0 to 8, with a higher score representing higher adherence to medication.

Table 2 Schedule of enrolment, interventions, and assessments

TIMEPOINT	STUDY PERIOD				
	Enrolment	Baseline T0	Intervention	Follow-up	
				T1	T2
ENROLMENT					
Eligibility screen	X				
Informed consent	X				
Allocation		X			
INTERVENTION					
Intervention group			X		
Control group			X		
ASSESSMENTS					
Primary outcome					
Medication adherence (Moresky-8)		X		X	X
Secondary outcomes					
Medication knowledge (PKMUQ)		X		X	X
Medication beliefs (BMQ)		X		X	X
Medication self-efficacy (SEAMS)		X		X	X
Treatment burden (TBQ)		X		X	X
Potential covariates					

Socio-demographics questionnaire)	(Patients	X
Number of prescribed medications (one-item question)		X
Depressive symptoms (PHQ-9)		X

Secondary

outcomes

Medication Knowledge

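### Short block lengths disclosed to the nurses who recruit and treat leave up to about 70% of assignments predictable, even if the list itself were hidden

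*Combined protocol and SAP*

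**What the plan says.** **Restriction.** Section 6, Randomization & blinding: "The design will use random block lengths of 2, 4 or 6, and include an initial unbalanced block", the initial block being "with a maximum of one additional patient in either arm, to further hide allocation sequences". The sequence is computer-generated by the Nursing/Midwifery Research department, but the same section then has the principal investigator and the clinical nurse specialists keep it. No strata are mentioned, so there is one list.

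**Masking.** Section 5: "This is a single Centre open label, two-arm randomized controlled trial with 1:1 randomization at the participant level". The Summary differs: "This study is a single centre, single-blind, two-arm randomised controlled trial". The only masking actually described is of outcome collection (Outcome assessment): "The nurses masked to the participant allocation will collect follow-up data through telephone interview". Nothing masks the recruiters.

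**Roles.** Section 6, Recruitment: "Three clinical nurse specialist as a part of research team from NCCCR will deliver the intervention", and "Nurses will recruit participants through approaching potentially eligible participants in NCCCR". The nurse specialists also arrange the centre appointments. Section 7, Informed Consent, again has them approach patients, and allows at least one week to decide before the enrolment visit.

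**Disclosure.** Nurses' training Intervention: "Nurses will also receive a detailed study protocol and a manual containing instructions for delivering the intervention". No provision withholds the block lengths from that copy.

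**The concern.** Permuted blocks bring the arms back to a fixed difference at the end of every block, here within at most six patients. Someone who knows the past assignments can bet on the arm that is behind. The nurses who deliver the sessions learn who was allocated to them, and they influence when a patient is booked.

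If likely assignments can be anticipated, more motivated patients could be brought forward when the intervention arm is due. The primary outcome is self-reported Morisky-8 adherence, so such selection would pass into the main comparison. Analysis by allocated arm does not remove it, because it happens before randomisation. Adjustment for baseline adherence would help little, because eligibility confines that score to the bottom of the scale (below 2 under Participants, zero in the inclusion criteria; the two differ).

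**Working it through.** The documents give no figure for predictability, so there is none to reproduce. The check takes only the sequence length from the sample-size section.

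**Inputs from the protocol:** N = 100; 1:1 allocation; one list; block lengths 2, 4 or 6; an initial block off balance by at most one patient.

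**Assumed, because not stated:** the three lengths equally likely; an initial block of 1, 3 or 5 patients.

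**Step 1, closed form without the initial block.** Guess the arm with fewer patients so far, and toss a coin when level. In a block of 2m the expected number of correct guesses is m + (2^(2m)/C(2m,m) - 1)/2.

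- Length 2: 1 + (4/2 - 1)/2 = 1.5, or 75.0%
- Length 4: 2 + (16/6 - 1)/2 = 2.833, or 70.8%
- Length 6: 3 + (64/20 - 1)/2 = 4.1, or 68.3%
- Equal mix: (1.5 + 2.833 + 4.1)/(2 + 4 + 6) = 8.433/12 = 70.3%

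The rule never uses the current block's length, so varying the lengths does not defeat it.

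**Step 2, simulated lists of 100 with the initial block.** The guesser knows the possible lengths but not the length of any given block, and updates by Bayes' rule.

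| Guesser or design | Correct | Callable at 75% or better |
|---|---|---|
| Plan as written, all assignments followed | about 69.6% | 56% |
| Plan, simple rule that learns the offset | 69.5 to 69.7% | not computed |
| Plan, offset ignored | 62% | not computed |
| Plan, each of three nurses sees only her own patients | 52% | not computed |
| Lengths 4, 6, 8 | 67.4% | 32% |
| Lengths 6, 8, 10 | about 66% | 24% |
| Big-stick rule, maximum imbalance 5 | 54.6% | not computed |
| Simple randomisation | 50% | 0% |

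Under the plan about 4% of assignments are known with certainty. Other block weights give about 68.6% to 71%. Without the initial block the simulated figure is about 70.1%, so the block costs a guesser who allows for it less than one point.

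**Step 3, effect of timing.** The table assumes that the guess is made for the very next assignment. If other patients are randomised in between, best-guess accuracy falls to about 58% (one patient), 55% (two) and 51 to 52% (three). Calls at 75% or better fall to about 10%, 1% and 0%. The accrual rate is not given, so the number intervening in a week is unknown.

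**Step 4, what longer blocks cost in balance.** The largest possible final difference is half the longest block plus the initial offset. For the plan it is 3 + 1 = 4 (52:48). For 6, 8, 10 it is 5 + 1 = 6 (53:47), and relative efficiency is then 4 x 0.53 x 0.47 = 0.996. Simple randomisation averages 0.990, with a 5th percentile of 0.96 (a 40:60 split).

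**The case against.** The strongest reply is that 70% describes an ideal observer. It needs someone who knows every earlier assignment in order, works out the offset, and controls who is next. The documents do not establish all three. Three nurses share delivery, controls receive no structured sessions, and nothing says that each nurse follows the others' patients. Without sharing the figure is 52%, little better than chance, and the initial block does hinder a naive guesser (62%). These limits stand. Sharing is nonetheless plausible, with three nurses at one centre and a principal investigator who meets the intervention nurses weekly.

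The one-week decision period also stands as protection at first approach. It protects less at booking or consent. The Recruitment section gives eligibility and consent to the principal investigator or a co-investigator, which would be a safeguard. However, Randomization & blinding gives the eligibility assessment to the nurse specialists, and the principal investigator also keeps the randomisation.

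A third reply is that the nurse specialists hold the list anyway, so block length is secondary. That is right, and it fixes the order of the changes. It does not remove the point, because securing the list would leave the short, disclosed blocks in place.

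A reader might go further and infer that selection bias could never be detected. The documents do not support that: beliefs, self-efficacy, knowledge, treatment burden and PHQ-9 are measured at baseline, and section 8 compares baseline characteristics and adjusts for baseline confounders. Motivation itself is not measured, so detection and correction would be partial.

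**Conclusion.** The point holds as an avoidable weakness that is cheap to reduce. With the list hidden, up to about 70% of assignments could be predicted by someone who follows all of them and acts at booking or consent; less complete knowledge gives 52% to 62%. The ceiling rests on the assumed block weights and initial block length, and moves only between about 68.6% and 71% when the weights change.

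Two stronger readings are not supported. One is that the nurses will know 70% of assignments: the figure is an average against a 50% baseline, and only about 4% are certain. The other is that permuted blocks must be abandoned: simple or big-stick randomisation is a legitimate trade-off, not a requirement. Nothing in the documents shows that selection has occurred.

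The open-label description relied on here is contradicted by the Summary. Because only the follow-up assessors are masked, the contradiction does not change the conclusion, but the two statements should be reconciled.

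**What to change.** 1. In Randomization & blinding, take the list out of the nurse specialists' custody. Without this the remaining changes gain nothing.
2. Delete block length 2 and use longer varied lengths, for example 6, 8 and 10. Calls at 75% or better fall from 56% to 24%, and accuracy from about 70% to about 66%.
3. Move the block lengths and the details of the initial block to a document held by the Nursing/Midwifery Research department, and remove them from the protocol copy given to nurses. On its own this achieves little, because the simple offset-learning rule reaches 69.5 to 69.7% without knowing the lengths. It belongs with item 2.
4. Optionally, at the statistician's preference, use simple randomisation or a big-stick rule with maximum imbalance 5.

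Items 2 and 3 cost a reprogrammed list and one protocol edit before first enrolment, plus a slightly larger possible imbalance (at most 53:47 instead of 52:48 with the example lengths). Simple randomisation would cost about 1% of efficiency on average. Longer blocks reduce the exposure but do not remove it.

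### The PI and CNS keep the randomisation and also approach, screen, consent and enrol patients, so allocation is not concealed and selection bias can enter

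*Combined protocol and SAP*

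**What the plan says.** Section 6, Randomization & blinding, describes how the sequence is made: "Randomization will be block randomization, and generated by a computer program centrally (Nursing/ Midwifery Research department". Permuted blocks of random length 2, 4 or 6 follow an initial unbalanced block, whose stated purpose is "to further hide allocation sequences". The same subsection then gives custody: "The randomization will be kept by the PI and CNS". Assignment takes place where patients are recruited: "Consenting participants will be randomized in outpatient clinic in NCCCR".

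The enrolment tasks are described in three places:

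- Section 6, Recruitment: "Nurses will recruit participants through approaching potentially eligible participants in NCCCR". Here the nurses are the three clinical nurse specialists who deliver the intervention. It continues: "the principal investigator/ co-investigator will determine the eligibility of participants, describe the study to them, obtain written consent forms, and collect baseline data".
- Section 6, Randomization & blinding: the CNS carries out the eligibility assessment.
- Section 7, Informed Consent: "the CNS will approach the patients directly based on the inclusion exclusion criteria". Patients then have a week to decide, after which the team contacts them to confirm.

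The available text describes no sealed envelopes, no telephone or web release and no independent holder of the list. The only stated masking of staff, under Outcome assessment in section 7, covers the nurses who collect follow-up data by telephone.

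**The concern.** Concealment means that nobody who decides whether a patient enters the trial can know the next assignment. Central generation protects how the sequence is produced, and random block lengths make it harder to guess. Neither helps if the people recruiting hold the sequence.

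A recruiter who knows the next arm has several points at which to act: whom to approach, how to read a borderline screening result, and how to handle the patient during the week allowed for a decision. The entry rules leave room for judgement, because section 6, Participants, gives two multimorbidity thresholds (three or more conditions, and at least two) and two Morisky thresholds (below 2, and exactly zero). Baseline scoring may also be exposed. Table 2 puts allocation and baseline assessment in the same T0 column, and nothing states that the questionnaires come first.

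More motivated patients could therefore be steered to the intervention. Motivation plausibly predicts later self-reported adherence and is not among the potential covariates in Table 2. Intention-to-treat keeps the arms as they were formed, so it preserves any such imbalance. Adjustment can act only on what is measured.

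**Working it through.** The plan states no figure on this point, so the main check sets the roles side by side.

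| Task | Who does it | Where stated | Keeper of the randomisation? |
|---|---|---|---|
| Generate sequence | Nursing/Midwifery Research department | 6, Randomization & blinding | Not named as keeper |
| Keep randomisation | PI and CNS | 6, Randomization & blinding | Yes |
| Approach and recruit | CNS | 6, Recruitment; 7, Informed Consent | Yes |
| Assess eligibility | PI or co-investigator | 6, Recruitment | Yes, if the PI |
| Assess eligibility | CNS | 6, Randomization & blinding | Yes |
| Consent and baseline data | PI or co-investigator | 6, Recruitment | Yes, if the PI |
| Deliver intervention | CNS | 6, Recruitment | Yes |
| Follow-up calls | Nurses masked to allocation | 7, Outcome assessment | Stated as masked |

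The two accounts of who assesses eligibility conflict. Under either one a keeper takes part in enrolment, because the CNS always makes the approach.

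**Predictability.** With the list in hand, the next arm is known 100% of the time, whatever the block lengths. For comparison, suppose the list is withheld but past assignments are known. A simulation of 100 patients (20,000 runs; block lengths 2, 4 and 6 assumed equally likely; initial unbalanced block omitted) used the rule of guessing the arm that is behind, with a coin toss when the arms are level. The guess was right about 70% of the time, against 50% by chance.

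**Effect on the test.** Inputs: n = 47 per arm (section 6, Sample size), two-sided α = 0.05, no treatment effect. The assumed input is a prognostic difference δ between arms, in SD units, caused by selection. For a two-sample t-test:

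- degrees of freedom = 2 × 47 − 2 = 92
- noncentrality = δ × √(47/2) = δ × 4.848
- rejection rate = P(|T| > t₀.₉₇₅,₉₂), with T noncentral t

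| Assumed δ (SD) | Noncentrality | Rejection rate | Simulation, 40,000 runs |
|---|---|---|---|
| 0 | 0 | 5.0% | 5.0% |
| 0.1 | 0.485 | 7.7% | 7.6% |
| 0.2 | 0.970 | 16.0% | 15.9% |
| 0.3 | 1.454 | 30.2% | 30.1% |

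The two methods agree within simulation error. Relative to the planned effect, 0.2 / 0.52 = 0.38, so a shift of 0.2 SD would be 38% of the difference the trial is designed to find.

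**The case against.** The strongest objection is about wording. The custody sentence does not mention a list, and it directly follows one about computer-generated participant codes. It could mean the record of assignments already made. That reading is possible, but the protocol does not state it and names no other holder of the upcoming sequence. Even on that reading, recruiters who know past assignments could guess the next with roughly 70% success under the assumptions above, and the sentence would still need correcting.

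Second, the plan already places allocation after consent in several places, and section 7 refers to a screening and randomisation tool whose content is not in the available text. Randomising after consent does not stop a list-holder from knowing the next arm while eligibility and consent are being settled. An unseen form cannot be counted as a safeguard against custody that the protocol states outright.

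Third, section 1 calls the trial single-blind (section 5 says open label), and the follow-up callers are masked. This limits bias in measuring the outcome. It does nothing about bias in who enters each arm.

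Four points stand and limit the claim:

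- The narrow Morisky entry range leaves little room for baseline differences on the primary scale itself, so the main risk is selection on unmeasured motivation.
- A co-investigator, not named as a keeper, may sometimes take consent.
- The size calculation uses an unadjusted t-test, whereas section 8 plans baseline-adjusted generalised estimating equations. The assumed shift is best read as what adjustment leaves behind.
- Independent custody would not remove guessing from known past assignments.

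**Conclusion.** The concern holds. As written, the plan gives the randomisation to people who recruit and screen, and nothing in the text offsets this. It defeats the plan's own aim of hiding the sequence. The role overlap is explicit. That bias will follow is a risk, not a certainty, and its size cannot be derived from the documents. The false-positive rates of 7.7%, 16.0% and 30.2% rest entirely on assumed shifts of 0.1, 0.2 and 0.3 SD. The title's feasibility label does not lessen the point, because the primary objective is effectiveness and the sample size targets 80% power. The damage could not be repaired after enrolment, so the text must change before the first patient is randomised.

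**What to change.** Replace the custody sentence in section 6, Randomization & blinding, with wording to this effect:

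> The allocation list is generated and held only by the Nursing/Midwifery Research department. The department releases one assignment at a time, by telephone, web or sequentially numbered opaque sealed envelope, after eligibility has been confirmed, consent signed and the baseline questionnaires completed. The PI, co-investigators, CNS and the nurses who make the T1 and T2 calls have no access to the list.

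Two edits should go with it. Table 2 should show baseline assessment before allocation, and the Recruitment and Randomization & blinding text should agree on who confirms eligibility. Because the CNS will learn each assignment once it is released, the block lengths should also be removed from the version that recruiters see, to limit guessing.

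The cost is a wording change, one call or envelope for each of about 100 patients, and a short wait at each assignment. Envelopes need no added staff. Telephone release requires the department to be reachable during clinics, which the documents do not address. The sample size and the analysis do not change.
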